### 16.1.2 Urine Variables

- Urine concentrations of galidesivir.
- Urine PK parameters of galidesivir.

Urine samples will be collected to determine the concentrations of galidesivir. The urine PK parameter summaries described in this section will be created using the PK population.

Urine PK Parameters		
Parameter	Description	Programming Notes
Ct1-t2	Concentration (of the unchanged drug) in the collection interval t1-t2.	Directly from data, no calculation required.  Measured in the clinic, captured on the CRF, no calculation required.
Vt1-t2	Volume of the urine collected in the interval t1-t2	

Urine PK Parameters		
Parameter	Description	Programming Notes
Aet1-t2	Amount of drug excreted unchanged into urine in the interval t1-t2, calculated as the urine volume times the urine concentration for each interval. Intervals: 0-12 h, 12-24 h, 24-48 h, 48-72 h, 72-96 h, 0-96h (cumulative)	$C_{t1-t2} * V_{t1-t2}$
% Dose excreted,t1-t2	Percentage of given dose excreted in the urine as unchanged drug Intervals: 0-12 h, 12-24 h, 24-48 h, 48-72 h, 72-96 h, 0-96h (cumulative)	$A_{et1-t2}/Dose * 100$ Dose will be converted to match units of Ae
CL r	Renal clearance of unchanged drug cumulatively over all collection intervals	$CL_r = Ae_{0-t1}/AUC_{0-t1}$ CL r parameter will be calculated according to time matched AUC.

Note: Urine PK parameters will be estimated in SAS based on the recorded urine concentrations and volumes. In estimating the parameters, all missing values will be recorded as missing and all BLQ values will be set to zero. If a missing value is encountered, the cumulative parameters will not be calculated for that subject.

## 16.2 Pharmacokinetic Summaries

### 16.2.1 Plasma Concentrations

Plasma concentrations for BCX4430 below the quantifiable limit (BQL) will be set to zero in the computation of mean concentration values. Descriptive statistics including n, arithmetic mean, SD, arithmetic CV%, geometric mean, geometric CV%, geometric n (the number of subjects with an observation who were included in the natural logarithmic transformation) median, min, and max will be used to summarize the plasma concentrations by treatment at each scheduled time point. If more than half of the subjects in a given cell have values BQL, then the descriptive statistics will not be presented and will instead display as BQL for the mean and minimum. Except for n and maximum, all other statistics will be missing. Any value less than BQL will be presented as BQL.

Linear and semi-logarithmic plots of the arithmetic mean and median plasma concentrations by scheduled sampling time will be provided by treatment. These plots will show time in hours. The plots will match the summary table results and will not have an observation at a given time point if more than half of the subjects have values BQL. Mean plots will include SD error bars when plotted on a linear scale and log scale.

Linear and semi-logarithmic plots of the individual plasma concentrations by actual sampling time will be provided by subject (1 subject per page). These plots will show time in hours. Individual plots will use the BQL handling procedure described below for "Plasma Pharmacokinetic Parameters".

All individual subject plasma concentration data will be listed by cohort and treatment.

### 16.2.2 Plasma Pharmacokinetic Parameters

Plasma PK parameters for BCX4430 will be estimated using non-compartmental methods with WinNonlin®.

The plasma PK parameters will be estimated from the concentration-time profiles. In estimating the PK parameters, BQL values at the beginning of the profile will be set to zero. BQL values that occur after the first quantifiable point will be considered missing. Samples that are BQL but are between two samples with detectable concentrations will be excluded from PK analysis.

Actual sampling times, rather than scheduled sampling times, will be used in all computations involving sampling times. If the actual time or dose time is missing, the scheduled time may be substituted in order to calculate the PK parameter.

Determination of points to be included in  $\lambda_z$  range will follow the Guideline for Defining, Calculating and Summarizing Pharmacokinetic / Pharmacodynamic Parameters (EDSREP 009 R 01) and rule will be noted in table and listing footnotes.

Descriptive statistics (n, arithmetic mean, SD, arithmetic CV%, geometric mean, geometric CV%, median, min, and max) will be used to summarize the calculated PK parameters by treatment. For  $T_{max}$ ,  $T_{lag}$ , and  $T_{last}$ , only n, median, min, and max will be presented.

Individual PK parameters AUCt, AUCinf, and Cmax with corresponding geometric means will be shown graphically for each treatment.

All individual subject PK parameters will be listed by treatment and period.

### 16.2.3 Urine Pharmacokinetic Parameters

Urine PK parameters will be estimated in SAS based on the recorded urine concentrations and volumes. In estimating the parameters, all missing values will be recorded as missing and all BLQ values will be set to zero. If a missing value is encountered, the cumulative parameters will not be calculated for that subject. Summaries of amounts excreted by treatment and scheduled collection interval (Aet1-t2), including cumulative amount excreted, fraction excreted by treatment and scheduled collection interval (% Doseexcreted,t1-t2), including cumulative fraction excreted, and renal clearance (CLr) will be provided. Descriptive statistics (n, arithmetic mean, SD, arithmetic CV%, geometric mean, geometric CV%, median, min, and max) will be used to summarize the calculated PK parameters by treatment.

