8.5. Replacement of Subjects

Replacement subjects may be enrolled as needed for the study to obtain the required number of evaluable subjects. An evaluable subject is defined as a subject who has sufficient PK samples collected to determine PK parameters through 24 hours post-dose and has sufficient safety data (including ECGs, ECHOs, vital signs, PE findings, and clinical lab data) through 24 hours post-dose to allow for the evaluation of the primary objective. At least 5 evaluable subjects who received galidesivir are required per cohort. Replacement subjects will be allowed if PK parameters (through 24 hours post-dose) cannot be determined due to a subject's early discontinuation from the study drug or study.

Subjects who have an IV infusion stopped for non-drug related issues, as described in Section [7.6.3.1](#), will not continue with dosing but will have all scheduled safety assessments made. These subjects may be replaced as needed. Subjects who have an IV infusion stopped for a safety related issued will not continue with dosing and will be followed as per Section [8.4.1](#). These subjects may be replaced if needed to fulfill the required number of evaluable subjects.

Subjects who withdraw due to a galidesivir-related AE will not be replaced. Subjects who withdraw for other reasons may be replaced at the discretion of the Investigator and Sponsor to ensure a sufficient number of evaluable subjects at the end of the clinical study.

Following the infusion, one subject per cohort may withdraw prior to the completion of Day 5 without being replaced. Should more than 1 subject from the same cohort who did not meet the above criteria voluntarily withdraw from the study, those subjects may be replaced.

In the event that a replacement subject withdraws, the subject will not be replaced.

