12.3.1.4. Pharmacokinetic Analysis

Concentrations of galidesivir will be determined by validated plasma and urine assays and will be summarized by treatment and displayed in figures. Plasma PK parameters for each subject will be estimated over the sampling interval using noncompartmental analysis (Phoenix WinNonlin Version 7.0 or higher, Certara) and summarized by treatment group using descriptive statistics. The amount and percentage of galidesivir excreted in the urine will be assessed at all doses. If possible, data will be summarized by cohort and dose proportionality assessed.

The PK parameters that will be estimated for galidesivir are listed in [Table 9](#). Additional analyses may be conducted as appropriate.

Table 9: Pharmacokinetic Parameters

Pharmacokinetic Parameter	Definition
AUC _{inf}	Area under the concentration versus time curve extrapolated to infinite time, calculated as AUC _{last} + (C _{last} /λ _z)
AUC _t	Area under the concentration versus time curve from time zero to time “t”; may be denoted as AUC _{last} if the “t” is the last timepoint with a measurable concentration
% AUC _{exp}	Percentage of AUC extrapolated between AUC _{last} and AUC _{inf}
C _{last}	Last measurable concentration of drug
C _{max}	Maximum observed concentration of drug
t _{1/2}	Estimate of the terminal elimination half-life of the drug
CL	CL = Dose/AUC where “Dose” is the dose of the drug and AUC = AUC _{inf}
λ _z	Terminal elimination rate constant, estimate by linear regression of the terminal elimination phase of the concentration of drug versus time curve
V _z	Volume of distribution of the drug
T _{max}	Time to C _{max}
CL _r	Renal clearance of unchanged drug in a specific interval (CL _r [interval]) or cumulatively over all collection intervals
% Dose _{excreted}	Percentage of given dose excreted in the urine as unchanged drug

In all derivations of PK parameters, zero will be substituted for concentrations below the quantitation limit (BQL) of the assay. Samples that are BQL, but are between two samples with detectable concentrations will be excluded from PK analysis.

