## 7.0 Overview of Planned Analysis

### 7.1 Changes from Protocol

There are no changes from the protocol.

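### One missed urine collection removes a subject's renal clearance, although the collected intervals with time-matched AUC would usually give a usable estimate

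*SAP*

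**What the plan says.** Urine is collected over five post-dose intervals: 0–12, 12–24, 24–48, 48–72 and 72–96 h (Protocol 11.2.2).

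SAP 16.1.2 lists a single renal clearance parameter, described as "Renal clearance of unchanged drug cumulatively over all collection intervals". The formula is Ae0–t1/AUC0–t1, with the note that the "parameter will be calculated according to time matched AUC". The footnote to that table and SAP 16.2.3 give the same missing-data rule: "If a missing value is encountered, the cumulative parameters will not be calculated for that subject".

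Protocol Table 9 (section 12.3.1.4) is wider. It defines CLr as "Renal clearance of unchanged drug in a specific interval" or cumulatively. The SAP does not carry over the interval form, and SAP 7.1 states "There are no changes from the protocol".

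The SAP does keep interval results for the other urine parameters. Section 16.2.3 plans "Summaries of amounts excreted by treatment and scheduled collection interval", and the same for percentage of dose.

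On missing subjects, Protocol 8.5 says: "Following the infusion, one subject per cohort may withdraw prior to the completion of Day 5 without being replaced". It counts a subject as evaluable on PK and safety data through 24 h, and requires at least 5 evaluable subjects on galidesivir per cohort.

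**The concern.** The missing-data rule treats three parameters alike that behave differently. Cumulative Ae and cumulative percentage of dose are sums, so leaving out an interval understates them, and declining to calculate them is sound. CLr is a ratio. If an interval is left out of both the amount and the AUC, what remains still estimates renal clearance over the time that was observed.

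A subject can be evaluable under Protocol 8.5 on 24 h of data and belong to the PK population (SAP 10.2 needs only one estimable parameter), yet have no CLr because one later container was lost. Urinary elimination is part of the secondary objective and each cohort has only 6 subjects on active drug, so each lost value counts.

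**Working it through.** The plan gives no figure on this point, so there is nothing to reproduce. The checks below ask how much of a subject's information the rule discards, and what the alternative would cost.

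**1. Share of exposure in each interval.** Inputs are the Cohort 2 (10 mg/kg) interim geometric means in the dose-escalation report appended to the SAP: AUC0–24 = 20,400 ng·h/mL, AUC0–inf = 32,400 ng·h/mL, t1/2 = 89.1 h. Then λ = ln 2/89.1 = 0.00778 per h. With a mono-exponential tail after 24 h, the AUC from a to b is (C24/λ) × [exp(−λ(a−24)) − exp(−λ(b−24))].

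C24 is not reported for this study, so I used two sources:
- Back-calculated: C24 = λ × (32,400 − 20,400) = 93.4 ng/mL.
- From the intramuscular study, Day 1 trough at 10 mg/kg (Protocol Table 4): 134 ng/mL, with 100–170 as an assumed range.

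| C24 (ng/mL) | AUC24–48 | AUC48–72 | AUC72–96 | AUC0–96 | 72–96 h share | 0–24 h share |
|---|---|---|---|---|---|---|
| 93.4 | 2,044 | 1,696 | 1,407 | 25,546 | 5.5% | 79.9% |
| 100 | 2,189 | 1,816 | 1,507 | 25,913 | 5.8% | 78.7% |
| 134 | 2,934 | 2,434 | 2,019 | 27,787 | 7.3% | 73.4% |
| 170 | 3,722 | 3,088 | 2,562 | 29,772 | 8.6% | 68.5% |

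If only 72–96 h is lost, 91–95% of the time-matched exposure was observed, yet the subject's CLr is discarded. The higher C24 values probably overstate the tail: 134 implies AUC0–inf of 20,400 + 134/λ = 37,625, against 32,400 reported.

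**2. Is a partial CLr valid?** If CLr is constant over 0–96 h, Ae in each interval is CLr × AUC in that interval. The sum of Ae over the collected intervals divided by the sum of AUC over the same intervals is then CLr, whichever intervals are missing. A simulation with an assumed 10% error per interval and C24 = 134 gave a mean estimate/true ratio of 1.000 for every pattern tried. The SD of that ratio was 6.7% with all five intervals, 7.2% without 72–96 h and 8.9% with 0–24 h only.

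**3. If CLr is not constant.** Let m be the missed share of AUC0–96 and r the ratio of CLr in the missed intervals to CLr in the others. The partial CLr differs from the 0–96 h CLr by 1/[1 − m(1 − r)] − 1. At C24 = 134:
- 72–96 h missing (m = 7.3%): +2.2% at r = 0.7, −3.5% at r = 1.5.
- All after 24 h missing (m = 26.6%): +8.7% at r = 0.7, −11.7% at r = 1.5.

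At C24 = 170 these become +2.7% to −4.1% and +10.4% to −13.6%.

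**4. The sums, for contrast.** Under constant CLr, adding only the collected intervals understates cumulative Ae and percentage of dose by 5.5–8.6% (72–96 h missing) or 20.1–31.5% (all after 24 h missing). No ratio cancels this, so the present rule is right for them.

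**5. Cost in n.** The 90% CI factor on a geometric mean is exp[t(0.95, n−1) × s/√n], with s = √ln(1 + CV²). The CVs of 16.5% and 42.2% are those of the urinary fraction in the intramuscular study (Protocol 4.3.1.2), used here as stand-ins for CLr. Going from n = 6 to 5 moves the factor from 1.14 to 1.17 (CV 16.5%) or from 1.40 to 1.47 (CV 42.2%).

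**6. How often.** If each interval is missing independently with probability p, a subject loses CLr with probability 1 − (1 − p)^5. That is 4.9%, 9.6%, 22.6% or 41.0% for p = 1%, 2%, 5% or 10%. The documents give no value for p.

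**The case against.** The best defence is that one common 0–96 h window keeps CLr comparable across subjects. Mixing windows gains n only by assuming that CLr is stable, which the documents do not state. Protocol Table 9 offers interval or cumulative CLr, so choosing the cumulative form is within the protocol. The interim reports need a caution too: the Cohort 2 report says its AUC values may be slightly underestimated, and that a subject with data only through 24 h was left out of the half-life and clearance means. All of this stands. It argues for flagging partial values and for treating the interval shares as illustrative, but not for discarding CLr outright.

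One might also read the t1 in the SAP formula as allowing a shorter window. The row's own description and the missing-value rule point the other way, and at best the programmer is left to choose.

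Three stronger readings are tempting, and the documents do not support them:

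- *Subjects with a missing interval drop out of the urinary-elimination results.* They do not. Their collected intervals stay in the per-interval Ae and percentage-of-dose summaries, and they stay in the PK population.
- *The partial estimate is unbiased.* Only if CLr is constant over time (steps 2 and 3).
- *The rule selectively removes subjects whose kidneys were affected.* The kidney was the principal target organ after IV infusion in animals, and Protocol 8.5 does not replace subjects who withdraw for a drug-related AE. But subjects are confined for 96 h (Protocol 7.1), those who stop study drug are to stay in the study (7.6.3.1), and an AE is not itself a listed reason for ending participation (8.4.1). A subject whose infusion is stopped is outside the PK population by a separate rule (9.7). Two of the appended cohort reports record no discontinuations. Renal safety is followed through creatinine, cystatin C, NGAL, UACR and urinalysis, none of which depends on this rule.

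Finally, SAP 16.2.3 plans descriptive statistics and no confidence interval for CLr, so step 5 only illustrates the loss of precision.

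**Conclusion.** The point holds for CLr only. As written, one missing urine concentration or volume removes a subject's CLr, even when over 90% of the matched exposure was observed. The rule is appropriate for cumulative Ae and cumulative percentage of dose.

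The consequence is mainly a smaller n for a descriptive secondary parameter, for example 5 instead of 6 in a cohort. Bias in the cohort mean would arise only if missingness were related to renal clearance, and nothing in the documents shows that it is. The interval shares rest on interim geometric means, a mono-exponential tail and an assumed C24; the frequency of loss rests on an assumed missingness rate. None of these assumptions affects the structural point that a ratio to a time-matched AUC does not need every interval. This is a minor improvement to the SAP and not a threat to the study's conclusions.

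**What to change.** In SAP 16.1.2 and 16.2.3:

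- Calculate CLr as the sum of Ae over the collected intervals divided by the sum of partial AUC over the same intervals, requiring complete 0–24 h data.
- Flag in the listing any subject with fewer than five intervals and give the window used.
- Keep the no-calculation rule for cumulative Ae and percentage of dose excreted over 0–96 h.
- State in SAP 7.1 how the CLr definition relates to Protocol Table 9.

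The cost is about two sentences and a small programming change. No new data are needed, because the plasma schedule already has samples at 12, 24, 48, 72 and 96 h. The downside is that flagged subjects have a different time window, with differences from the 0–96 h CLr of the size in step 3 if CLr varies over time. A subject missing 0–12 or 12–24 h would still have no CLr. That limit is deliberate, since 0–24 h carries roughly 68–80% of AUC0–96.

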### 16.2.4 Dose Proportionality Analyses

#### 16.2.4.1 Power Model

The assessment of dose proportionality for the PK parameters of BCX4430 will use a power model approach (including all doses). A model with ln-transformed dose (dose continuous) as a fixed effect and subject as a random effect will be applied to the following ln-transformed PK parameters: AUCt, AUCinf, and Cmax. Although there is no formal statistical hypothesis tested for this secondary objective, there will be evidence for dose-proportionality for each PK parameter if the 90% confidence interval (CI) of the fixed slope for ln-dose contains 1. No adjustment for multiplicity will be performed for the set 3 of PK parameters.

The SAS pseudo code for the power model is as follows:

```
data adpp;
set adpp;
ln_auc = log(auc);
ln_dose = log(dose);
run;

proc mixed data=adpp method=reml;
by parameter;
class subject;
model ln_auc = ln_dose / ddfm=kr ci alpha=0.1;
random subject;
run;
```

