4.4.3. Rationale for Study Doses

The initial dose levels for galidesivir in this study were selected on the basis of the PK and safety data from Study BCX4430-101 together with target exposures effective in animal models of MVD. The PK of galidesivir was well characterized in Study BCX4430-101 after both single and multiple ascending doses; this enabled the dose selection for this study to be made on the basis of simulated efficacious exposures in models of MVD and other filovirus infections. The simulations of MVD model efficacious exposures were based on pharmacokinetic studies in cynomolgus macaques and corresponding effective doses in the same species in a model of MVD. Simulations of human exposure after IV infusion administration have suggested that exposure will be similar to the observed following the IM administration of galidesivir. The 5 mg/kg dose selected as the starting dose for this study is anticipated to have a C_{max} of approximately 3000 ng/mL and an AUC from time 0 to 24 hours (AUC₂₄) of approximately 10,000 ng.h/mL. The proposed maximum dose for this study, a single dose of 20 mg/kg, is also supported by the nonclinical safety and TK data for IV administration in monkeys and rats, with a no adverse effect level (NOAEL) in monkeys of 30 mg/kg/day with an associated AUC₂₄ of 52,500 ng.h/mL; the expected human exposure at a 20 mg/kg dose is approximately 47,000 ng.h/mL.

All planned proposed doses for the study are in Section 7.1. The choice of higher doses to be studied may be modified depending on emerging PK results from the lower dose cohorts.

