#### 9.4.3.2 Secondary Objective – Dose Proportionality

Dose proportionality for  $AUC_{inf}$ ,  $AUC_t$ , and  $C_{max}$  will be evaluated using the power model (including all doses) and also using an ANOVA model where each dose will be compared with a reference dose in a pairwise basis. The mean slope from the power model and the set of pairwise comparisons from the ANOVA method will constitute descriptive evaluations of dose proportionality.

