**Equation 2:**

$$Y_{ik} = \alpha \times \text{Dose}^{\beta}$$

where  $\alpha$  includes the error.

Dose proportionality for PK parameters will be assessed by restricted maximum likelihood using SAS PROC MIXED. The mean slope will be estimated from the power model and the corresponding 90% CI calculated. If the 90% CI of the slope of the  $C_{max}$  and AUCs contains 1, then dose proportionality is indicated.

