**Analysis of Variance**

Following log-e transformation, dose-normalized PK parameters will be analyzed with an ANOVA model using PROC MIXED. Each dose will be compared with a reference dose on a pairwise basis. The ratio of geometric least squares means (LSM) and the corresponding 90% CI will be estimated for each PK parameter of interest. If the 90% CI for the geometric LSM ratio for a given pairwise comparison falls completely within the 0.8 to 1.25 equivalence region then dose proportionality is indicated.

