## 16.0 Pharmacokinetic Variables

### 16.1.1 Plasma Variables

- Plasma concentrations of galidesivir.
- Plasma PK parameters of galidesivir.

Venous blood samples will be collected to determine the plasma concentrations of BCX4430. The plasma concentration summaries and figures with mean values described in this section will be created using the safety population. The plasma PK parameter summaries and statistical analyses described in this section will be created using the PK population.

Plasma PK Parameters		
Parameter	Description	Programming Notes
AUC inf	Area under the concentration versus time curve extrapolated to infinite time, calculated as $AUC_{last} + (C_{last}/\lambda_z)$	AUCINF_obs from WNL  If valid lambda_z is not present, then parameter is flagged in listings and will not be used in summary statistics.
AUC t	Area under the concentration versus time curve from time zero to time "t"; may be denoted as AUC last if the "t" is the last timepoint with a measurable concentration	AUClast from WinNonlin If actual time deviates >20% from nominal time, then AUC t will be flagged in listings and will not be used in statistical analyses. If valid $\lambda_z$ is not present, then AUC t is flagged in listings and will not be used in statistical analyses.
% AUC exp	Percentage of AUC extrapolated between AUC last and AUC inf	AUC_%Extrap_obs from WinNonlin Listed only
C last	Last measurable concentration of drug	Clast from WinNonlin If actual time at T last deviates >20% from nominal time, then parameter is flagged in listings and will not be used in summary statistics.
T last	Time of last measurable concentration of drug	Tlast from WinNonlin If actual time at T last deviates >20% from nominal time, then parameter is flagged in listings and will not be used in summary statistics
C max	Maximum observed concentration of drug	C max from WinNonlin

Plasma PK Parameters		
Parameter	Description	Programming Notes
$t_{1/2}$	Estimate of the terminal elimination half-life of the drug	HL_Lambda_z from WinNonlin  If valid $\lambda_z$ is not present, then parameter is flagged in listings and will not be used in summary statistics.
CL	CL = Dose/AUC where "Dose" is the dose of the drug and AUC = AUC inf	CL_obs from WinNonlin

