#### 16.2.4.2 ANOVA Model Pairwise Comparisons

Following log-e transformation, dose-normalized PK parameters will be analyzed with an ANOVA model using PROC MIXED. Each dose will be compared with a reference dose on a pair-wise basis. Pairwise

comparisons of the ratio of GLS means and the corresponding 90% CI will be estimated for each PK parameter of interest. Although there is no formal statistical hypothesis tested for this secondary objective, if the 90% CI for the geometric LSM ratio falls completely within the 0.8 to 1.25 equivalence region then dose proportionality is indicated for the specific comparison. No adjustment for multiplicity will be performed for the set of descriptive pairwise comparisons.

The SAS PROC MIXED pseudo code for the pairwise comparison for the ANOVA model is as follows:

```
data adpp;
set adpp;
ln_auc_dose = log(auc)/dose;
run;

ods output diffs=diffs;
ods output lsmeans=lsmeans;
proc mixed data=adpp method=reml;
by parameter;
class dose;
model ln_auc_dose = dose / ddfm=kr;
lsmeans dose / pdiff alpha=0.1 cl;
run;
```

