**8.0 PK Summary (insert tables, appendices as allowed by sponsor, if available):**

Subjects in the table below have been anonymized with an alphabet code. Given the way the cohort dosing was staggered and that samples through only 24 hours post dosing were available for one subject in the cohort, only geometric mean data is presented in order to maintain the blind. If the subject received active, their half-life and clearance parameters are not included in the mean.

Additionally, the  $C_{max}$  for 3 subjects was greater than 10000 ng/mL (the upper limit of quantitation in the assay) and there was not time to re-assay prior to the dose escalation meeting. Therefore, it is possible that the AUC and  $C_{max}$  parameters are slightly underestimated. The anticipated geometric mean  $C_{max}$  for this cohort was approximately 10000-11000 ng/mL, so it is not anticipated that the  $C_{max}$  concentrations are much greater than 10000 ng/mL, or that the AUC parameters are significantly higher than calculated below.

[figure not shown]
No PK parameters met halting rules, and overall, the PK following a 10 mg/kg single dose administered by IV infusion was in line with anticipated exposure based on modeling and simulation and the exposure in Cohort 1 (5 mg/kg dose). Furthermore, the simulated exposure for the next two dose levels is not anticipated to exceed the PK stopping criteria in the protocol.

	T $\frac{1}{2}$ (h)	$C_{max}^*$ (ng/mL)	AUC 0-24h (ng.h/mL)	AUC 0-last (ng.h/mL)	AUC 0-inf (ng.h/mL)	%AUC extrap	Cl (mL/h/kg)	Vz (mL/kg)
Geomean	89.1	9240	20400	30200	32400	11.1	285	36600
%CV	21.6	10.6	12.8	14.1	20.9	41.5	14.2	35.4

\* 3 subjects had a  $C_{max}$  > 10000 ng/mL

The figure below shows the mean galidesivir concentration-time profiles for the first two cohorts of this study.

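### A 90% CI for the power-model slope that contains 1 is read as dose proportionality, though it only fails to reject slope = 1 and can conflict with the SAP's own ANOVA rule

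*SAP*

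**What the plan says.** Dose proportionality is a secondary endpoint (Protocol Section 6.2; SAP Section 5.2.1), assessed on AUCinf, AUCt and Cmax by two methods.

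- **Power model.** SAP Section 16.2.4.1: "there will be evidence for dose-proportionality for each PK parameter if the 90% confidence interval (CI) of the fixed slope for ln-dose contains 1". Section 9.4.3.2 states the rule more firmly: if the 90% CI of the slope "contains 1, then dose proportionality is indicated". Neither section limits the width of the interval.
- **ANOVA on dose-normalised parameters.** SAP Section 9.4.3.2 requires that the 90% CI of the geometric mean ratio "falls completely within the 0.8 to 1.25 equivalence region then dose proportionality is indicated". Section 16.2.4.2 applies this to each comparison separately. No reference dose is named.
- **Status.** SAP Section 9.4.3.2 says that the slope and the pairwise comparisons "will constitute descriptive evaluations of dose proportionality". Sections 16.2.4.1 and 16.2.4.2 add that no formal hypothesis is tested.
- **Protocol.** Sections 12.3.1.5.1 and 12.3.1.5.2 ask only for the estimates and their 90% CIs. Both decision rules were added in the SAP.

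**The concern.** A 90% CI contains 1 exactly when a two-sided 10% test does not reject slope = 1. This is absence of evidence against proportionality, yet the SAP reports it as evidence for it. At a true slope of exactly 1 the rule is met 90% of the time whatever the precision. At any other slope it is met more often as the data get noisier or fewer.

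The ANOVA rule works the other way, because imprecise data cannot fit inside 0.8 to 1.25. The slope uses all doses and the ANOVA takes one pair at a time, so some difference is expected. Here, though, opposite logic drives the verdicts apart, and the SAP does not say how a split result is to be read.

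The stake is the conclusion reported for a named secondary endpoint. Dose escalation does not depend on it, since the PK escalation criterion is a median AUC24 threshold (Protocol Sections 7.6.2 and 11.5.2). Protocol Section 11.5.3 asks that PK rise in proportion to dose before any cohort is added after Cohort 4, but does not cite this rule.

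**Working it through.** The documents give no power or error rate for this endpoint, so there is no stated figure to reproduce.

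**Inputs**

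- Design: 6 galidesivir subjects at each of 5, 10, 15 and 20 mg/kg, one dose each (SAP Section 6.0).
- CVs from the 10 mg/kg IV cohort (dose-escalation PK summary filed with the SAP): Cmax 10.6%, AUC0-24 12.8%, AUClast 14.1%, CL 14.2%, AUCinf 20.9%. The Cmax figure is probably understated, because 3 subjects exceeded the assay limit.
- Upper scenario: 30%, from Cmax after IM dosing (25.7% to 37.0%, Protocol Table 3).
- Assumptions: log-normal data and the same CV at every dose. The ANOVA follows the SAP text (log of the dose-normalised parameter, pooled variance, 20 df), with 5 mg/kg as reference.

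**Why 20.9% is treated as an upper scenario.** CL is dose divided by AUCinf, so on a per-kg basis the two CVs should match, but they are 14.2% and 20.9%. The means disagree as well: 10 mg/kg ÷ 285 mL/h/kg = 35,100 ng·h/mL, against a reported AUCinf of 32,400. The summary says of one subject with samples only to 24 hours: "If the subject received active, their half-life and clearance parameters are not included in the mean". If five subjects have a geometric mean of 35,088 and six have 32,400, the sixth value is 32,400^6 / 35,088^5 = 21,750, close to the cohort AUC0-24 of 20,400. That fits one short profile left out of CL but kept in AUCinf. It is an inference, because individual values are not shown.

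**Slope CI**

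- Sxx = Σ(ln dose − mean)² = 6.505; df = 22; t(0.95) = 1.717; σ = √ln(1 + CV²).
- Half-width = 1.717 σ / √6.505 = 0.673 σ.
- P(CI contains 1) comes from the noncentral t distribution with noncentrality (β − 1)√6.505 / σ.

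| CV | Half-width | β = 1 | β = 1.116 | β = 1.2 |
|---|---|---|---|---|
| 10.6% | 0.071 | 90% | 14% | 0.1% |
| 12.8% | 0.086 | 90% | 27% | 1.3% |
| 14.2% | 0.095 | 90% | 35% | 3% |
| 20.9% | 0.139 | 90% | 60% | 23% |
| 30% | 0.198 | 90% | 74% | 48% |

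A slope of 1.2 means a dose-normalised ratio of 4^0.2 = 1.32 for 20 versus 5 mg/kg. The slope of 1.116 comes from Protocol Section 4.4.3, which expects about 10,000 ng·h/mL at 5 mg/kg and says "the expected human exposure at a 20 mg/kg dose is approximately 47,000 ng.h/mL": ln(47,000/10,000) / ln 4 = 1.116, a 1.175-fold departure. This lies inside 0.8 to 1.25, so its column does not show false verdicts. It shows the same drug receiving different verdicts according to precision.

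**Disagreement with the ANOVA at true slope 1** (20 versus 5 mg/kg, 400,000 simulated trials per setting)

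| CV | Slope passes, ANOVA fails | Slope fails, ANOVA passes |
|---|---|---|
| 10.6% | 2% | 6% |
| 12.8% | 13% | 3% |
| 14.2% | 23% | 1% |

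If failing any of the three comparisons with 5 mg/kg counts as ANOVA failure, the first column becomes 10%, 33% and 51%.

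**One worked case in the reverse direction.** Take CV 10.6% and an estimated slope of 1.08. The slope CI is 1.08 ± 0.071 = 1.009 to 1.151, which excludes 1. The ratio CIs against 5 mg/kg are 0.951–1.174, 0.983–1.213 and 1.006–1.241, all inside 0.8 to 1.25. The slope rule withholds proportionality while every ANOVA comparison indicates it.

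**The case against.** The strongest reply is that little follows from the rule. Both analyses are labelled descriptive, the slope and CI are reported anyway, and no dosing, safety or primary-endpoint decision uses the verdict. At the CVs seen for most IV parameters (10.6% to 14.2%), a true slope of 1.2 is called proportional in at most 3% of trials. The large rates come from 20.9%, which is probably inflated, and 30%, which comes from IM injection. All of this stands and limits the consequence. It does not rescue the rule, because a descriptive analysis needs no verdict and the SAP prescribes one in evidential terms.

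Three narrower points also stand:

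- The 12.8% CV is for AUC0-24, and the 1.116 slope rests on approximate exposure projections stated or judged on the AUC24 scale. AUC0-24 is not one of the three analysed parameters. These inputs only illustrate how the verdict moves with precision.
- The CVs come from one small cohort. Around 14.2%, the 90% CI is about 9.5% to 30% with 5 df, or 9.2% to 34% with 4 df if one subject was indeed left out of CL.
- The disagreement rates assume the ANOVA as described in the text. The pseudo-code in SAP Section 16.2.4.2 divides the log by dose instead of taking the log of the dose-normalised value, which is a separate defect. Run as written, it would not apply the 0.8 to 1.25 rule.

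The earlier IM study openly reported that the two methods differed for Cmax (Protocol Section 4.3.1.2). That shows conflicts arise and can be reported side by side, but the SAP does not require it, and that study's decision rules are not given.

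**Conclusion.** The concern holds. As written, the power-model rule turns non-rejection into a finding of proportionality, and for any true slope other than 1 it favours imprecise data. The error is small if the CVs stay at 10.6% to 14.2% (a slope of 1.2 passes in 0.1% to 3% of trials) and substantial at 20.9% (23%) or 30% (48%). Even for a truly proportional drug, the two rules disagree on 20 versus 5 mg/kg in about 9%, 15% and 25% of trials at CVs of 10.6%, 12.8% and 14.2%. These figures rest on six evaluable subjects at each of four doses, log-normal data, equal CVs and 5 mg/kg as the reference. The change should be made, but its effect is limited to how a secondary endpoint is reported.

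**What to change.** In SAP Sections 9.4.3.2 and 16.2.4.1, delete the verdict based on the interval containing 1 and report the slope with its 90% CI as a descriptive result. Add a sentence saying that the slope and the pairwise ANOVA results are read together and that any disagreement is reported as such. This is a wording change in two places. It matches Protocol Section 12.3.1.5.1 and needs no amendment.

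If a verdict is wanted, carry the SAP's own margin over to the slope. Proportionality is indicated only if the 90% CI lies wholly within 1 + ln(0.8)/ln(r) to 1 + ln(1.25)/ln(r), where r is the ratio of the highest to the lowest dose studied. The limits are 0.839 to 1.161 for r = 4 and 0.797 to 1.203 for r = 3. A CI wholly outside the limits is non-proportional, and anything else is inconclusive.

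The optional rule has costs:

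- A truly proportional parameter meets it in 97%, 86%, 76% and 23% of trials at CVs of 10.6%, 12.8%, 14.2% and 20.9%.
- A slope of 1.2 is called non-proportional in only 23%, 19%, 17% and 12% at those CVs; most of the other results are inconclusive. At CV 10.6% it is called proportional in 0.5%, slightly more than the 0.1% under the current rule.
- Total disagreement with 20 versus 5 mg/kg at true slope 1 falls from 9% to 4%, 15% to 10% and 25% to 14% at CVs of 10.6%, 12.8% and 14.2%. At CV 10.6%, slope passing while ANOVA fails rises slightly, from 2% to 3%.

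Some disagreement therefore remains, so the sentence on reading the two results together is needed either way.
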